3.1 General Design

This study is a Phase II open label study of daily administration of sirolimus in up to 24 evaluable male or female adults. Up to 40 subjects may be enrolled, defined as providing informed consent for the trial, to obtain this target of evaluable subjects. An interim analysis will be conducted after 14 subjects have completed the Visit 9 intermediate assessment. The mechanism of action of sirolimus in clinically active iMCD will also be examined.

Adult subjects will receive a sirolimus loading dose of 5 mg/m², rounded to the nearest mg, on day 1. Loading dose may be lower at the discretion of the prescribing physician. Starting on day 2, adult subjects will take sirolimus daily at 2.5 mg/m²/day (rounded to the nearest mg), adjusted to a target trough level of 10-15 ng/mL. Pediatric subjects will not receive a loading dose, and daily dosing will be at 2 mg/m²/day (rounded to the nearest mg), adjusted to achieve a target trough level of 5-15 ng/mL. (see **Section 5.2, Intervention Regimen**). Given that sirolimus is extensively metabolized by CYP3A4, sirolimus dosing for subjects receiving strong CYP3A4 inhibitors or inducer therapy (https://drug-interactions.medicine.iu.edu/main-table.aspx) should be monitored carefully and adjusted accordingly. Additionally, sirolimus trough levels should be monitored if patients are started on or if their CYP3A4 therapy is altered, and sirolimus dosing adjusted to maintain trough levels of 10-15 ng/mL (5-15 ng/mL in children). The dosing of adult patients who weigh less than 40 kg should be adjusted, based on body surface area, to 3

mg/m² for the loading dose and 1 mg/m²/day daily. It is recommended that the licensed site investigator reduce maintenance dose in patients with hepatic impairment.

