4.1 Inclusion Criteria

To be eligible, subjects must meet all of the below inclusion criteria:

- 1. Male or female, age 2-80
- Documented disease history consistent with the diagnostic criteria for iMCD (Appendix 15.1)
 - Confirmation of clinico-histopathological features by licensed pathologist, or a CAS grade of at least 3 in the companion registry study (ACCELERATE)
- 3. Failed/refractory (patient did not achieve sufficient disease control with anti-IL-6 therapy, as determined by the site investigator), relapsed (return of symptoms while on therapy), or inability to tolerate anti-IL-6 or anti-IL-6 receptor therapy
- 4. Evidence of active disease, defined as at least two abnormalities in the criteria comprising the CBR criteria and as defined as abnormal by CTCAE v4.0, including at least one objective measurement (hemoglobin, weight loss, or lymph node size)
 - Hemoglobin < lower limit of normal
 - Fatigue, including fatigue relieved by rest
 - Anorexia, including loss of appetite without alteration in eating habits
 - Fever or night sweats
 - Weight loss ≥ 5% from baseline
 - At least one lymph node meeting modified Cheson criteria (**Appendix 15.2**)
- 5. Ability to consume oral medication in the form of a tablet
- 6. Ability to provide, or for a LAR to provide on their behalf, informed consent prior to any study-specific activities

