4.5 Total Number of Subjects and Sites

Up to 40 subjects may enroll into this study to achieve the intended goal of up to 24 evaluable subjects. To determine if the trial will continue, an interim analysis will be completed after 14 subjects have completed the Visit 9 intermediate assessment. This trial involves up to four sites, which are expected to have approximately equal enrollment rates.

4.6 Vulnerable Populations:

Children 2 years of age or older may be considered for this study. Pregnant women, fetuses, neonates, and prisoners are not included in this research study.

5 Study Intervention

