7.6 Efficacy Evaluations

The below measures will be used to assess the efficacy of the study intervention and determine if the subject meets criteria for a CBR. All comparisons are against those obtained during the Baseline Visit:

Positive response: Relative to baseline, improvement in at least one of the below criterion without worsening of any single criterion other than hemoglobin on two consecutive study visits.

Negative response: Relative to baseline, worsening of any single criterion other than hemoglobin on two consecutive site visits or failure to achieve improvement for any criterion.

	Hemoglobin	Fatigue	Anorexia	Fever and night sweats	Weight	Lymph node size
Improvement	≥2 g/dL increase without transfusions	≥1 grade decrease by NCI CTCAE version 4.0, May, 2009	≥1 grade decrease by NCI CTCAE version 4.0, May, 2009	≥2°C decrease in fever or return to normal body temperature (37°C) or improvement in night sweats, as assessed by licensed site investigator	≥5% increase not due to increase in new or existing edema	≥25% decrease bi-dimensionally in size of largest lymph node, as measured using Cheson criteria (Appendix 15.2)
Worsening		≥2 grade increase by NCI CTCAE version 4.0, May, 2009	≥2 grade increase by NCI CTCAE version 4.0, May, 2009	≥2°C increase in fever or worsening in night sweats, as assessed by licensed site investigator	≥5% decrease (weight loss not due to decreased edema)	≥25% increase bidimensionally in size of largest lymph node, as measured using Cheson criteria (Appendix 15.2)

The below table provides the CHAP score, which will be used to assess the efficacy of the study intervention. All comparisons are against those obtained during the Baseline Visit:

Score:	0	1	2	3	4
CRP (mg/dL)	<1	≥1, <5	≥5, <10	≥10, <20	≥20
Hemoglobin (g/dL)	≥12	<12, ≥10	<10,≥8	<8	Transfusion dependent
Albumin (g/dL)	≥3	<3,≥2.5	<2.5, ≥2	<2, ≥1.5	<1.5
Performance Score (ECOG)	0	1	2	3	4

The below table provides the modified Cheson response criteria, which will be used to assess the efficacy of the study intervention. Unless otherwise specified, all comparisons are against those obtained during the Baseline Visit:

Complete Response (CR)	All index lesion(s) must have regressed to normal size (≤1.0 cm in		
	their greatest transverse diameter. No new sites of		
	lymphadenopathy >1.5 cm in longest dimension.		
Partial Response (PR)	≥50% decrease in sum of the products of the greatest diameters		

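### CBR scores a weight gain of at least 5% as improvement at every age, so a growing child with otherwise unchanged disease can be counted a 12-month responder

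*Combined protocol and SAP*

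**What the plan says.** Section 7.6 has one CBR table for all subjects. Weight improves with at least a "5% increase not due to increase in new or existing edema" and worsens with a fall of at least 5% not due to decreased edema. Both are measured from the Baseline Visit. A positive response requires "Relative to baseline, improvement in at least one of the below criterion". The condition attached to this is that it must occur "without worsening of any single criterion other than hemoglobin on two consecutive study visits". No age limit, percentile or growth correction is attached to the weight criterion. Weight also need not be abnormal at entry: inclusion criterion 4 in 4.1 asks for any two CBR abnormalities, at least one of them objective.

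Sections 3.2.1 and 8.1 make the proportion with a positive CBR at 12 ± 1 month the primary endpoint. Section 8.6 analyses every dosed subject at each visit completed.

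Children are admitted. Section 4.1 has "Male or female, age 2-80", 4.6 has "Children 2 years of age or older may be considered for this study", and 3.1 gives paediatric dosing ("Pediatric subjects will not receive a loading dose"). Two passages suggest that there may be few: 3.1 also speaks of "up to 24 evaluable male or female adults", and 4.1 requires "Ability to consume oral medication in the form of a tablet".

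**The concern.** In an adult with this disease, a 5% weight gain without edema is a reasonable sign of benefit. In a child, some gain over a year is expected whatever the drug does. Because one criterion suffices and the baseline is fixed, the rule as written cannot separate growth from response.

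The same feature works in the other direction. A child who stops growing, or who loses less than 5% of baseline weight, shows no weight worsening, although the shortfall against expected weight may be much larger.

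The design does little to expose such cases. Section 8 sets the null at 0% activity, 8.5.1 tests CBR against historic placebo data, and there is no concurrent control arm in which growth-only responses would appear. With at most 24 evaluable subjects, one misclassified child is visible in the estimate. Section 8 also lets the trial continue past the interim on a single positive CBR among 14 subjects at Visit 9.

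**Working it through.** **Inputs from the documents.** Threshold 5% of baseline weight (7.6); primary assessment at 12 ± 1 month (8.1); interim at Visit 9, month 6, after 14 subjects (6.2.7, 8); maximum 24 evaluable (8.4).

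**Inputs assumed.** The documents give no growth rates. I use 1, 2 and 3 kg a year, and 0.5 kg a year as a slow case because these children have active disease.

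**The plan's own figure.** The interim size of 14 follows from the zero-response rule: 0.8^13 = 0.0550 and 0.8^14 = 0.0440, so 14 is the smallest n below 0.05 at a 20% response rate. This point does not alter that figure.

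**Who reaches 5% through growth.** With gain g kg a year, the largest baseline weight that reaches 5% by month m is g × (m/12) / 0.05.

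| Assumed gain (kg/year) | Month 12 | Month 9 | Month 6 | Month 3 |
|---|---|---|---|---|
| 0.5 | 10 kg | 7.5 kg | 5 kg | 2.5 kg |
| 1 | 20 kg | 15 kg | 10 kg | 5 kg |
| 2 | 40 kg | 30 kg | 20 kg | 10 kg |
| 3 | 60 kg | 45 kg | 30 kg | 15 kg |

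The visit window moves the month-12 limits by 1/12, or 8.3%, either way. At 2 kg a year the limit is 2 × (11/12)/0.05 = 36.7 kg at month 11 and 2 × (13/12)/0.05 = 43.3 kg at month 13.

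**If improvement must also hold on two consecutive visits.** The sentence in 7.6 can be read to apply the two-visit condition to worsening only, or to improvement as well. Section 6.2.10 lists no physical examination or vital signs at Visits 13 and 14, so the preceding examination before Visit 15 is Visit 12 (month 9). The month-9 column then governs the primary endpoint: 15, 30 or 45 kg at 1, 2 or 3 kg a year. Visits 7 and 8 likewise list none, so for Visit 9 the month-3 column governs: 5, 10 or 15 kg, against 10, 20 or 30 kg on the looser reading.

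**Example: 20 kg child, month 12.** Gains are 0.5/20 = 2.5%, 1/20 = 5.0%, 2/20 = 10.0% and 3/20 = 15.0%. The slow case does not qualify; the other three do.

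**Weight of one misclassified child.** 1/24 = 4.2 points on the final proportion; 1/14 = 7.1 points at the interim. The addition is zero if the child also improves on another criterion.

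**Masked worsening.** A 20 kg child scores as worse on weight at 19 kg or below. Against an expected weight of 20 + g, the shortfall needed at month 12 is 1 − 19/20.5 = 7.3%, 1 − 19/21 = 9.5%, 1 − 19/22 = 13.6% or 1 − 19/23 = 17.4% for 0.5, 1, 2 or 3 kg a year. The fall must also be present on two consecutive visits.

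**The case against.** The strongest reply is that the effect may not occur. The number of children is not stated and could be zero. A growth-only responder must also improve on none of the five other criteria (one needs only a one-grade drop in fatigue), worsen on none, and remain on study to month 12, although 6.4 and 6.6 let the investigator remove a subject for progression or at discretion. Weight may even be missing: 7.3 does not name it among the vital signs, and 6.2.11 performs the examination and vital signs only if Visit 15 is on site. All of this stands. It limits the size of the problem but does not correct the rule, since stable disease does not force withdrawal.

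There are partial safeguards. The DSMB may adjudicate final outcome (9.7.2), but this is optional and carries no growth rule. CHAP, the Cheson criteria and the 34-item symptom score give no credit for weight gain, but they are secondary endpoints and do not change the primary count. Section 1.1 calls CBR established, citing its Phase I use, but shows nothing about its behaviour in growing children.

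A sensitivity analysis excluding weight-only paediatric responders would expose any inflation without redefining the endpoint. That is true, but it would leave the primary count and the masked worsening as they are.

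Two stronger readings are tempting. First, since one of four sites is a children's hospital and 4.5 expects roughly equal enrolment, a reader might take 24/4 = 6 subjects to be children and note that 5/24 = 20.8% already exceeds the 20% activity level. The documents give no age mix, and each of these children would have to respond on growth alone. Second, a reader might infer that growth defeats the interim rule, or that the stricter two-visit reading removes the risk. Neither follows: the limits at Visit 9 confine any effect to small children, and 10 and 15 kg at 2 and 3 kg a year remain under the stricter reading. Passing the interim also only permits further enrolment.

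**Conclusion.** The gap is real but narrow. As written, 7.6 allows ordinary growth to produce a positive 12-month CBR in a child whose disease is otherwise unchanged, and it does not score failure to gain weight as worsening. This rests on the text and holds on either reading of the two-visit condition; only the weight limits change.

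The size is unknown and may be nil. On the assumed 1, 2 or 3 kg a year, the children at risk are those up to 20, 40 or 60 kg at baseline (15, 30 or 45 kg if the gain must also be present at month 9), at 4.2 points per growth-only responder with N = 24. An effect on the interim rule is less likely under the stricter reading, but not excluded. The documents do not support saying that the response rate will be inflated, or by how much, and adult scoring is unaffected. The reference to adults in 3.1 and the scope of the two-visit condition are separate drafting points on which this conclusion does not depend.

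**What to change.** In 7.6, for paediatric subjects, with the age boundary stated by the sponsor, apply the existing 5% thresholds to observed weight relative to the weight expected at that visit had the child kept the baseline weight-for-age z-score. Name one growth reference before analysis. As an illustration, if a 20 kg child were expected to weigh 22 kg at month 12, improvement would need 22 × 1.05 = 23.1 kg and worsening would be 22 × 0.95 = 20.9 kg, instead of 21 kg and 19 kg now.

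If no reference is adopted, state that weight gain alone cannot qualify a paediatric subject as a CBR responder. This removes the false responders but leaves masked worsening uncorrected.

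In either case, report CBR under the rule as it now stands as a sensitivity analysis, and leave the adult rule unchanged.

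The cost is a change of wording in 7.6 and one derived variable. Gender and date of birth are recorded at screening (6.1.1) and weight is a CBR component, although it has to be obtained when a visit is remote. The downsides are a possibly slightly lower response rate, a small departure from the Phase I CBR definition in children, and no credit for resumed growth that only keeps the baseline z-score, even where the untreated child would have fallen below it.

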	(SPD) of index lesion(s), and no new sites of lymphadenopathy >1.5		
	cm in longest dimension.		
Stable Disease (SD)	Failure to achieve a CR or PR (see above) without evidence of		
	progressive disease (see below).		
Progressive Disease (PD)	≥50% increase from nadir in the SPD of any index lesion, or		
	appearance of any new sites of lymphadenopathy that measure >1.5		
	cm in longest dimension during or at the end of therapy.		

MCD-related Overall Symptom Score: In addition to the defined CBR, 34 measures of disease activity will be prospectively evaluated and graded (as per CTCAE version 4.0, May, 2009), which will be used to assess the efficacy of the study intervention. All comparisons are against those obtained during the Baseline Visit:

General MCD-related

- Fatigue
- Malaise
- Hyperhidrosis
- Night sweats
- Fever
- Weight loss
- Anorexia
- Tumor pain
- Dyspnea
- Pruritis

Autoimmune phenomena

- Autoimmune disorder
- Immune system disorder

Fluid retention

- Generalized edema
- Edema face
- Edema limbs
- Edema trunk
- Genital edema
- Localized edema
- Neck edema
- Periorbital edema
- Capillary leak syndrome

- Ascites
- Pleural effusion
- Pericardial effusion

Neuropathy

- Peripheral motor neuropathy
- Peripheral sensory neuropathy
- Nervous system disorder, other

Skin disorders

- Rash acneiform
- Rash maculo-papular
- Papulopustular rash
- Purpura
- Skin hyperpigmentation
- Skin induration
- Skin disorder, other

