15.2 Modified Cheson Criteria

Lymph node selection: Up to six dominant lymph nodes ("index lesions") should be selected according to the following features:

- they should be clearly measurable in at least two perpendicular dimensions, ≥1.0 cm in the long axis, and ≥1.0 cm in the longest perpendicular transverse dimension to the long axis
- they should be from as disparate regions of the body as possible and chosen such that they are representative of the subject's disease
- they should include mediastinal and retroperitoneal areas of disease whenever these sites are involved

Lymph node measurement: The long axis and the longest perpendicular transverse dimension to the long axis of each lymph node should be measured (together, the greatest diameters).

Calculating lymph node response:

CBR response criteria: The largest of the index lesions selected at baseline should be analyzed to determine CBR response.

Positive Response: ≥25% decrease in the product of the greatest diameters, as compared to the same lymph node at baseline.

Negative Response: ≥25% increase in the product of the greatest diameters, as compared to the same lymph node at baseline.

Example: If at baseline, the long axis = 3.0 cm and the longest perpendicular transverse dimension = 2.0 cm, then the baseline value calculated for this node would be 6.0. To achieve a positive response, the node would have the shrink so that that product of the two measurements is ≤ 4.5 . (e.g. 2 cm x 2.25 cm).

Cheson response criteria: all index lesions should be considered. When determining response, nodal measurements should be calculated independently and as the sum of the product of the greatest diameters, as described in (**Section 7.6 Efficacy Evaluations**).

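### The modified Cheson table scores only index lesions and new sites, so a complete response can be declared while unselected nodes that were enlarged at baseline persist or grow

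*Combined protocol and SAP*

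**What the plan says.** Lymph node response by the modified Cheson criteria is a secondary endpoint (Sections 3.2.2 and 8.2). Its categories are in the Section 7.6 table:

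- **CR:** "All index lesion(s) must have regressed to normal size" (≤1.0 cm in greatest transverse diameter), with no new site above 1.5 cm.
- **PR:** a fall of at least 50% in the sum of products of diameters, restricted to index lesions: "SPD) of index lesion(s), and no new sites of lymphadenopathy >1.5" cm.
- **SD:** the remainder: "Failure to achieve a CR or PR (see above) without evidence of" progression.
- **PD:** "≥50% increase from nadir in the SPD of any index lesion, or" the "appearance of any new sites of lymphadenopathy that measure >1.5" cm.

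Appendix 15.2 sets the index lesions: "Up to six dominant lymph nodes". They must be at least 1.0 cm in both dimensions, come from regions as far apart as possible, represent the subject's disease, and include mediastinal and retroperitoneal disease where present. No minimum number is stated. For the Cheson response the appendix says that "all index lesions should be considered" and does not mention other nodes.

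**The concern.** Index lesions are a sample of the nodal disease, whereas a complete response is a statement about all of it. The diagnostic criteria in Appendix 15.1 require enlarged nodes in at least two stations, so a subject may well have more enlarged nodes than index lesions. The table has no place for the remainder.

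The rule is also uneven. A new node just above 1.5 cm blocks CR and PR and is progression. A node present at baseline that grows well beyond that size changes nothing if it was not selected.

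At stake is the meaning of the nodal categories. Section 8 names the modified Cheson criteria among the assessments used to judge activity. With at most 24 evaluable subjects, one misclassified subject moves a proportion by 1/24 = 4.2 percentage points.

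**Working it through.** The plan states no figure for this point. Its one worked node example (15.2) is consistent: 3.0 × 2.0 = 6.0, and 75% of 6.0 is 4.5 = 2 × 2.25.

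**Step 1: apply the table literally.** The node sizes are assumptions. Six index nodes are 3.0 × 2.0 cm at baseline (SPD 6 × 6.0 = 36.0). Four further enlarged nodes of 2.5 × 2.0 cm are not selected (SPD 4 × 5.0 = 20.0). The total is 56.0, and no new site appears. The transverse diameter is taken as the second dimension.

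| Case | Index nodes | Unselected nodes | Total SPD | Table returns |
|---|---|---|---|---|
| a | 1.2 × 0.9 cm; SPD 6 × 1.08 = 6.48 | unchanged; SPD 20.0 | 26.48 (−53%) | CR |
| b | as in a | 4.0 × 3.0 cm; SPD 4 × 12.0 = 48.0 (+140%) | 54.48 (−2.7%) | CR |
| c | unchanged; SPD 36.0 | as in b | 84.0 (+50%) | SD |

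In (a), CR is declared with four nodes still 2.0 cm across. In (b), CR is declared although total nodal burden has hardly changed. In (c), growth of four nodes is not progression.

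**Step 2: what changes if unselected nodes count.** In (a), the index SPD has fallen by 1 − 6.48/36.0 = 82%, so the subject moves from CR to PR and remains a responder if response means CR or PR. In (b), the subject moves from CR to PD and is lost as a responder. In (c), SD becomes PD, a non-responder either way. A CR+PR rate is therefore inflated by pattern (b), not by persistence alone. There is one narrow exception. A node at the 15.2 minimum of 1.0 cm is already at the CR limit, so very small index nodes could normalise without halving the SPD. Such a subject would move from CR to SD.

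**Step 3: can the CR over-call be sized?** Assume ten enlarged nodes, node j normalising with probability p_j, and a common latent-normal correlation ρ. Then

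P(all normalise) = ∫ ∏ Φ[(Φ⁻¹(p_j) + √ρ·z)/√(1−ρ)] φ(z) dz.

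| p, index / unselected | ρ | CR on six | CR on all ten | Gap (points) |
|---|---|---|---|---|
| 0.80 / 0.80 | 0.3 | 39.4% | 27.5% | 11.9 |
| 0.80 / 0.80 | 0.6 | 52.1% | 44.1% | 7.9 |
| 0.80 / 0.90 | 0.3 | 39.4% | 34.2% | 5.3 |
| 0.70 / 0.90 | 0.3 | 24.5% | 22.1% | 2.4 |
| 0.70 / 0.95 | 0.6 | 37.8% | 37.6% | 0.2 |

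Gaps are taken before rounding. With six or fewer enlarged nodes, all selected, the gap is zero. Every input here is an assumption. The direction is fixed, because CR on a subset cannot be rarer than CR on all nodes, but the size is not.

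**The case against.** The selection rules in 15.2 (dominant, far apart, representative) are meant to make index lesions stand for the whole, and capping the number measured is a deliberate economy. If dominant nodes are the hardest to normalise, unselected nodes will usually follow them, and the gap shrinks to about 0.2 to 5 points in the model above. This stands as an argument about size. It does not give an unselected node a category.

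Three stronger readings are tempting, and the documents do not support them.

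- **The response rate is inflated by about 8 to 12 points.** That figure concerns CR alone, under equal normalisation probabilities. The endpoint is a proportion with a lymph node response, which the plan does not restrict to CR.
- **One index node may be chosen out of many.** In the ten-node model, a single index node gives CR in 80%, against 28 to 44% on all nodes, a gap of 36 to 52 points. No minimum is stated, but choosing one node of ten would ordinarily conflict with the rules on separate regions and representativeness.
- **Growth of unselected nodes can never be progression.** Appendix 15.2 remarks that masses which coalesce usually indicate PD or a technical problem, without limiting this to index lesions, and new sites are not defined. The remark concerns merging and sets no growth threshold, so it narrows the gap without closing it.

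Progression as judged by the site investigator (Section 6.6) is a ground for withdrawal and does not set the Cheson category. Central radiology review (Section 6) can only apply the rules it is given.

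**Conclusion.** The point holds as a defect in the definition of a secondary endpoint. Applied as written, the table can return CR while unselected baseline nodes persist or grow, and growth of those nodes meets no stated PD criterion apart from the remark on coalescing masses. It can over-call CR relative to PR. Leaving aside very small index nodes, it inflates a CR+PR rate only when unselected nodes progress while index nodes respond.

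The size cannot be estimated from the documents, which give neither the number of enlarged nodes per subject nor the frequency of discordant growth. The effect is confined to subjects with more enlarged nodes than were selected. A reader might infer that the main efficacy result is compromised. It is not: primary CBR uses only the largest index lesion and does not use this table, and no Cheson-specific test or decision threshold is planned.

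**What to change.** **Appendix 15.2.** When six or fewer nodes qualify, make all of them index lesions. When more qualify, record the remaining baseline nodes that meet the 15.2 size criteria as non-index, and have the central reader assess them qualitatively at each scheduled scan.

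**Section 7.6.**

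- CR also requires every non-index node to be ≤1.0 cm in greatest transverse diameter.
- PR also requires no unequivocal progression of non-index nodes.
- PD also includes unequivocal growth of a non-index node, for example a ≥50% increase in its product of diameters, measured only when growth is suspected.

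Measuring every non-index node in two dimensions at every scan is not needed and would largely defeat the six-lesion cap.

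**Cost.** No extra imaging is required, since the scans are already reviewed centrally. The change adds slightly more reading time and a CRF field, and the CR rate may be lower.
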